4 SUBJECT SELECTION

4.1 Patient Population

Severe emphysema patients indicated for Coil System treatment per the approved, CE marked IFU who meet the study inclusion and exclusion criteria, will be eligible to participate in the study.

4.2 Subject Selection

Recruitment will come from centers across Europe experienced in Coil System treatment and interventional bronchoscopy procedures that have affiliated physicians who have successfully completed the PneumRx Training program. The Coil procedure will be performed only at hospitals that have met the site qualification requirements for use of the Coil System as defined in the Coil training program and the study protocol. Additional qualification requirements include the ability to conduct the study per the approved protocol and demonstrated conduct of PFT, 6MWT, SGRQ, mMRC Dyspnea Scale testing in accordance with American Thoracic Society (ATS)/European Respiratory Society (ERS) standards.

Up to 30 centers across Europe will be invited to participate. Sites will be selected based on their experience with Coil technology, expertise in interventional bronchoscopy and operational and multidisciplinary resource availability.

Each center's PI, or a primary implanter, will perform all Coil treatments in the study if possible. If necessary, a secondary implanter will be trained as a back-up for situations in which the primary implanter is unavailable.

Pregnancy test need to be performed for females of child-bearing potential prior to radiographic procedures at baseline and implant procedures.

4.2.1 Inclusion Criteria

The study population will include all subjects who have met the inclusion criteria:

1. Read, understood and signed the Informed Consent form
2. Meets indications for use per the IFU
3. Bilateral heterogeneous and/or homogeneous emphysema
4. $15\% \text{ predicted} \leq \text{Post bronchodilator Forced Expiratory Volume in 1 second (FEV1)} \leq 45\% \text{ predicted}$
5. Post bronchodilator Residual Volume (RV) $\geq 200\% \text{ predicted}$
6. Post bronchodilator Total Lung Capacity (TLC) $>100\% \text{ predicted}$
7. Post bronchodilator RV/TLC $> 55\%$
8. Dyspnea ≥ 2 on modified Medical Research Council (mMRC) dyspnea scale despite optimal medical management
9. Receiving optimal drug therapy and medical management according to clinical practice.
10. Performing regular physical activity, at least 2 times per week ³
11. Stopped smoking as confirmed by carboxyhemoglobin (CoHB)
12. $100\text{m} \leq 6 \text{ minute walk distance (6MWD)} \leq 450\text{m}$
13. Deemed eligible per Eligibility Review Committee (ERC)
14. If treated in France, Subject must be entitled to French social security

4.2.2 Exclusion Criteria

The study population will not include any subjects who have met any of the exclusion criteria.

1. Known sensitivity to drugs required for performing bronchoscopy or in whom bronchoscopic procedures are contraindicated
2. Evidence of active infection in the lungs
3. Hypersensitivity or allergy to nitinol (nickel-titanium) or its constituent metals
4. Clinically significant pulmonary fibrosis
5. Clinically significant, generalized bronchiectasis
6. Clinically significant bleeding disorders
7. Patient taking immunosuppressive drugs other than steroids (e.g., for the treatment of cancer, rheumatic arthritis, autoimmune disease, or prevention of tissue or organ rejection).
8. Primary diagnosis of asthma
9. Two (2) or more COPD exacerbations in the prior year, or 1 or more COPD exacerbations in the prior 3 months with indication for hospitalization assessment, according to GOLD 2017 recommendations⁴⁵.

³ The World Health Organization defines physical activity as any bodily movement produced by skeletal muscles that requires energy expenditure – including activities undertaken while working, playing, carrying out household chores, travelling, and engaging in recreational pursuits. For those with limited mobility, this should be done at least 2 days per week.

⁴ Global Strategy for the Diagnosis, Management and Prevention of COPD, Global Initiative for Chronic Obstructive Lung Disease (GOLD) 2018

10. Predominant small airways disease defined as significant bronchiectasis with sputum production (> 2 tablespoons daily) or significant bronchial wall thickening per High Resolution Computed Tomography (HRCT)
11. Percent Low Attenuation Area (%LAA) < 20% in the most damaged lobe of either lung.
12. Computed Tomography (CT) Imaging consistent with active pulmonary infection, significant interstitial disease or pleural disease
13. Severe bullous disease (defined by bulla > 1/3 of lung volume, or single bullous defect > 8cm) or significant paraseptal emphysema [defined by numerous large (>1cm) paraseptal defects in the target lobe comprising >5% of total lung volume].
14. , or Lung pathology of nodule not proven stable or benign Radiographic confirmation of atelectasis or other scarring/fibrosis in areas of intended Coil implant
15. Use of more than 20 mg/day prednisone (or equivalent dosage of a similar steroid) daily
16. Severe pulmonary hypertension (Right Ventricular Systolic Pressure (RVSP) > 50 mm Hg (preferably measured by right heart catheterization) or other signs of Pulmonary Hypertension (PHT) with right ventricular dysfunction)
17. Severe hypercapnia ($\text{PaCO}_2 > 55$ mmHg on room air) and/or severe hypoxemia ($\text{PaO}_2 < 45$ mm Hg on room air, High altitude criterion: $\text{PaO}_2 < 30$ mm Hg)
18. Previous Lung Volume Reduction (LVR) surgery, lung transplantation, lobectomy, LVR devices or other device to treat COPD in either lung.
19. Diagnosed with alpha-1 antitrypsin deficiency
20. Diffusion Capacity of the Lungs for Carbon Monoxide (DLCO) < 20 %
21. Significant, recent or unstable cardiac disease defined as severe heart failure (Left Ventricular Ejection Fraction (LVEF) < 45% despite optimal medical management), unstable cardiac arrhythmia or coronary artery disease (angina on activity), or ischemic event in the past 6 months
22. Body Mass Index (BMI) > 30.
23. Participation in any other clinical study.
24. Subject is pregnant or lactating, or plan to become pregnant within the study timeframe.
25. If treated in France, Subject is a “personne vulnérable” as defined by French regulation.

4.3 Subject Crossover

Control group Subjects will be eligible for crossover to Treatment as soon as possible. Control subjects will be eligible for crossover if they still meet all inclusion and exclusion criteria, and if the patient is deemed to benefit from the Coil treatment by the investigator, based on best medical judgment. Crossover subjects will continue in the study through 36 months from first Coil implant. If Control subjects do not crossover to treatment, they will exit the study immediately.

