3.2 Trial Design

This is a prospective, multicenter, open label, randomized (2:1), controlled study comparing outcomes in subjects treated with the Coil System (Treatment) to a medically-managed control group (Control). Control group patients will be eligible for treatment with Coils (Crossover) 6 months after entry into the study.

The study is anticipated to begin enrollment early 2018. All subjects randomized to Treatment will be followed for 36 months post initial treatment. Subjects randomized to Control will be eligible for crossover as soon as possible. Crossover subjects will then be followed for 36 months post initial treatment. The anticipated last patient visit is expected in first half of 2023. If Control subjects choose not to crossover to treatment, they will exit the study immediately.

The data in this study, including Subject characteristics, outcome measures (e.g., health-related QOL, pulmonary function, exercise capacity), and safety (SAEs and specific respiratory AEs of interest), will be collected via the use of an electronic data capture (EDC) system on electronic Case Report Forms (eCRFs).

No biological samples will be taken other than blood draws taken at screening, and no biological samples will be stored for the study.

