5.1.3 Post-implant Management

Prophylactic regimen of medications should be administered according to the IFU and standard of care (SoC).

Per the IFU, a chest X-ray or still fluoroscopy image should be done post-procedure to verify Coil placement and to ensure there is no pneumothorax. A second, confirmatory chest X-ray should be done before discharge a minimum of 4 hours following the first chest X-ray. The second, confirmatory X-ray must be two views, posterior anterior (PA) and Lateral.

The Subject will be counseled on expected side-effects of the Coil procedure, including the potential AEs listed in Section 7.7. The Subject will be instructed to contact the treating physician immediately should any of the potential AEs be experienced. It is particularly important that Subjects be instructed at discharge to contact their implanting physician if they experience symptoms that may be indicative of pneumonia or CAIRS/CAO, to ensure that appropriate treatment is delivered.

Follow-up visits should be conducted per the schedule below. Study specific follow -up visits should take place during exacerbation free periods defined as 30 days with symptoms within normal day to day variability.

Treatment Group Subjects:

Visit	Visit window
Baseline visit	Eligibility, inclusion
Randomization	
First coil treatment	No more than 45 days post baseline visit
Second coil treatment	2 months +/- 4 weeks post first procedure
12-month follow-up	12 months +/- 4 weeks post first procedure
36-month follow-up	36 months +/- 4 weeks post first procedure

Control Group Subjects:

Visit	Visit window
Baseline visit	Eligibility, inclusion
Randomization	
First coil treatment	
Second coil treatment	2 months +/- 4 weeks post first procedure
12-month follow-up	12 months +/- 4 weeks post first procedure
36-month follow-up	36 months +/- 4 weeks post first procedure

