5.1.4 Duration of Treatment and Follow up

All Subjects randomized to Treatment will be followed for 36 months post initial treatment. Subjects randomized to Control will be allowed immediate treatment and will be followed for 36 months post initial treatment. If Control Subjects do not crossover to treatment, they will exit the study immediately.

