6.4.1 Baseline Visit

After the Subject provides informed consent, the Subject will be evaluated to ensure they are appropriate candidates for use of the Coil System. Eligibility to enroll in the study is assessed as described in Section 4.2.

The following evaluations will be performed as part of the Baseline visit.

- Informed Consent
- Demographic Information
- Medical history information, including comorbidities, smoking status, previous treatments of emphysema and baseline characteristics, physical activity, rehabilitation status
- Medications
- Pulmonary Function Test (PFT)
- Six Minute Walk Test (6MWT)
- Modified Medical Research Council mMRC dyspnea scale will be completed.
- QoL assessments: SGRQ, CAT, and EQ5D will be completed
- Blood gas, including CoHB for smoking cessation confirmation
- Blood test including cardiac panel with BNP test and other biomarker, if available
- Pregnancy test for females of child-bearing potential prior to radiographic procedures
- Echocardiogram
- Vital signs
- Inspiratory and expiratory HRCT (Note: a HRCT scan (inspiratory and expiratory) performed within 6 months prior to baseline may be used if it was acquired per the PneumRx QCT service protocol.)
- Chest X-Ray.

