6.4.2 Procedure/Implant Visit

Enrolled Subjects randomized to the either arm will undergo the Coil Treatment in accordance with the approved (CE Mark) IFU. Procedure visits will include 2 sessions: treatment procedure for one lung, followed by treatment procedure for the contralateral side lung, which should be scheduled approximately 2 months following the initial procedure.

The following evaluations will be performed for each procedure visit:

- Pregnancy test for females of child bearing-potential prior to radiographic procedures
- Treatment date
- Duration of bronchoscopy procedure
- Duration of fluoroscopy
- Duration of hospital stay
- Lung lobe and location treated
- Number and size of implanted Coils
- Procedural SAEs (see Section 7)
- Device malfunctions
- Prophylactic medications (antibiotics, steroids – including dosage and start/stop dates)
- Fluoroscopy image immediately post procedure – should be captured in eCRF
- Chest X-ray (PA and Lateral) before discharge at least 4 hours following the fluoroscopy image

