6.5.8 Eligibility Review Committee

Data from subjects who have signed the ICF and are considered by the treating physician to be eligible to receive the Coil treatment as part of the trial, should be submitted to the ERC for final assessment of eligibility for the study. The ERC will review the data in accordance with the procedures agreed to in the ERC Charter.

The ERC will consist of a minimum of 5 interventionalists. The purpose of the ERC is to provide peer-review from interventionalists who are extremely knowledgeable in the procedure and patient selection to confirm eligibility and suitability of subjects selected for participation in the ELEVATE trial. The ERC shall provide the final decision with regard to enrollment.

Data that will be provided to the ERC for review include PFT, medical history, and HRCT with QCT data. Two (2) of the 5 ERC members will be selected via random number generation. A member may decline to evaluate a subject file; in this case another member will be randomly selected. If 2 members agree to either approve or deny enrollment, that decision will be final. If the 2 members disagree, then a third, randomly selected member will independently review the case to determine eligibility. ERC members will document the reason for denial if the subject is not deemed not eligible for the study. The process will be blinded, such that a member receiving a request for review will not know how others have voted. An ERC member cannot review his /her own subject, in which case another ERC member will be randomly selected to review the data.

The determination of study eligibility will be recorded on the relevant eCRF.

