8.5 Efficacy Analyses

All effectiveness analyses will be analyzed on the ITT population through the 6-month visit, using descriptive statistics to summarize results separately for treatment and control groups. No comparative inferential statistics will be conducted. In addition, descriptive statistics will summarize percent change in FEV₁ from baseline to 12 and 36 months for all coil treated subjects. Baseline will be defined as the last measurement taken prior to coil treatment.

Descriptive statistics will summarize effectiveness endpoints at 12, 24 and 36 months follow-up.

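### Crossover requires Controls still to meet all criteria, but no check is scheduled and the sections conflict on timing, window and whether the condition applies

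*Combined protocol and SAP*

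**What the plan says.** Section 4.3 sets the condition for crossover: "Control subjects will be eligible for crossover if they still meet all inclusion and exclusion criteria". It adds the investigator's judgment that the patient will benefit. ERC eligibility is inclusion criterion 13 in Section 4.2.1, so it belongs to the condition. Section 6.5.8 says of this committee: "The ERC shall provide the final decision with regard to enrollment".

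Two other sections describe treatment of Controls without the condition:
- Section 5.1.4: "Subjects randomized to Control will be allowed immediate treatment and will be followed for 36 months post initial treatment".
- Section 6.4.2: "Enrolled Subjects randomized to the either arm will undergo the Coil Treatment in accordance with the approved (CE Mark) IFU".

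On timing, Section 3.2 says: "Control group patients will be eligible for treatment with Coils (Crossover) 6 months after entry into the study". The Design entry of the synopsis agrees. The Timelines entry of the synopsis, the next paragraph of Section 3.2 and Section 4.3 instead make Controls eligible at the earliest opportunity.

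On the window, the Treatment table in Section 5.1.3 gives the first coil treatment as "No more than 45 days post baseline visit", while the Control table leaves that cell empty. The schedule in Section 1, headed for both groups, attaches the same 45-day limit to Treatment 1.

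Two further provisions matter. Section 6.4.1 accepts an HRCT "performed within 6 months prior to baseline may be used". Section 8.5 sets the analysis baseline: "Baseline will be defined as the last measurement taken prior to coil treatment".

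**The concern.** A condition that subjects must still satisfy needs current data. Here an implant procedure depends on such a condition, and the schedule gives a site no visit at which to verify it. A site working only from Section 5.1.4 or 6.4.2 would not meet the condition at all. Section 2.1 describes emphysema as progressive, so eligibility findings and the CT used for lobar targeting can go out of date.

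There is also an analysis consequence. Section 8.5 summarizes 12- and 36-month FEV1 change for all coil-treated subjects together. If a crossover subject has no PFT after the original baseline, the change includes the untreated waiting period. For a Treatment subject that period is at most 45 days.

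**Working it through.** The only reproducible figure near this point is the allocation: 120 × 2/3 = 80 Treatment and 120 × 1/3 = 40 Control, as Section 8.1 states. No sample-size or power figure is in question.

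**Step 1. Can the condition be checked from scheduled data?** Before a Control's first implant, Section 1 marks PFT, 6MWT, the questionnaires with mMRC, HRCT and the baseline assessment (including echocardiogram and blood gas) at Baseline only. The treatment visits carry medications, adverse events, a pregnancy test and post-procedure imaging. Section 6.5.14 places HRCT at Baseline, 12 and 36 months. Criteria on pregnancy, medication and recent events could therefore be rechecked from data collected at or before the implant visit. Criteria on FEV1, RV, TLC, dyspnea, walk distance, CoHB, blood gases, DLCO, RVSP, LVEF and CT could not. ERC review is placed before randomization (Sections 6.1 and 6.5.8), and no second review is described.

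**Step 2. Are the timing rules compatible?** Inputs: 6 months (Section 3.2), 45 days (Section 1), and 1 month = 365.25/12 = 30.44 days.
- 6 months = 182.6 days.
- Excess over the limit: 182.6 − 45 = 137.6 days.
- Ratio: 182.6 / 45 = 4.06.

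A Control crossing over at 6 months cannot meet the Section 1 limit from the original baseline. Following both rules needs either a new baseline, which no section schedules, or a window specific to Controls, which Section 5.1.3 leaves blank.

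**Step 3. Age of data on the 6-month reading, with nothing measured after baseline.** The oldest permitted HRCT is 6 months old at baseline (Section 6.4.1), and 45 / 30.44 = 1.5 months.

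| | Treatment, maximum | Control crossing over at 6 months |
|---|---|---|
| PFT and other eligibility data at first implant | 45 days | about 183 days |
| HRCT at first implant | 6 + 1.5 = 7.5 months | 6 + 6 = 12 months |
| Baseline to 12-month visit | 12 + 1.5 = 13.5 months | 12 + 6 = 18 months |
| Baseline to 36-month visit | 36 + 1.5 = 37.5 months | 36 + 6 = 42 months |

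The last two rows use nominal visit dates. The 4-week tolerance moves them by 28 / 30.44 = 0.9 month either way.

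**Step 4. Reach into the pooled FEV1 summary.** If all 80 Treatment subjects and n Controls are implanted, the crossover share is n / (80 + n): 40/120 = 33%, 30/110 = 27%, 20/100 = 20%.

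The documents give no rate of untreated FEV1 change, so its effect can only be illustrated. Assume a drift d before implant of 0% to −5% and a true change after implant of g = +10%. The recorded change is (1 + d)(1 + g) − 1:
- d = 0%: 1.00 × 1.10 − 1 = +10.0%
- d = −2%: 0.98 × 1.10 − 1 = +7.8%
- d = −5%: 0.95 × 1.10 − 1 = +4.5%

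Both d and g are assumptions.

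**The case against.** The strongest reply is that Section 4.3 governs. It says the criteria must still be met, Section 10.2.6.2 makes the principal investigator responsible for conformity, and confirming the condition from old data would breach it. Section 5.1.4 is about duration of follow-up and Section 6.4.2 about the content of procedure visits, and neither expressly waives the condition. Operating detail may sit in the ERC Charter, the IFU or the separate analysis plan named in Section 8.2. This reply has force against any prediction that sites will ignore the condition. It does not supply the missing assessment or settle which of the conflicting statements a site should follow.

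Three stronger readings are tempting, and the documents do not support them.
- **No time limit for Controls.** Section 1 nominally applies 45 days to both groups. The finding is a conflict with the blank cell in Section 5.1.3, and a blank cell does not mean an unlimited interval.
- **Data always 6 or more months old.** This holds only on the 6-month reading with no later measurement. If crossover was immediate, the interval could be shorter.
- **A biased FEV1 result.** Section 8.5 applies one rule to everyone, the last measurement before the coil. Section 6.2 mentions core-laboratory review of 6-month PFT data, and FEV1 at 6 months is a co-primary endpoint. A Control with such a test has a recent FEV1 baseline. The current schedule contains no 6-month visit, however, and a later PFT would not refresh the CT, the echocardiogram or the ERC review.

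The affected summary is also descriptive, since Section 8.5 rules out comparative inference.

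**Conclusion.** The point holds as a failure to put the Section 4.3 condition into operation, together with contradictions among operative sections. No assessment is scheduled between the original baseline and a Control's first implant, no repeat ERC review is described, and two sections omit the condition. The 6-month crossover rule exceeds the 45-day limit about fourfold when counted from the original baseline.

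The data ages (about 6 months for eligibility data, up to about 12 months for HRCT) and the 18- and 42-month spans rest on two assumptions: crossover at 6 months from baseline, and no later measurement. At most 40 of 120 coil-treated subjects, one third, are exposed. Whether the FEV1 summary is distorted, and by how much, cannot be determined from the documents. The illustration runs from no effect to 5.5 percentage points in an affected subject (10.0 − 4.5), on assumed inputs throughout.

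**What to change.** - **Reconcile** the synopsis and Sections 1, 3.2, 4.3, 5.1.3, 5.1.4 and 6.4.2 on when crossover may occur, which baseline-to-treatment window applies to Controls, and whether treatment is conditional. Have Sections 5.1.4 and 6.4.2 refer to Section 4.3.
- **State in the schedule** how and when the Section 4.3 condition is verified, and whether ERC review is repeated. The clinical content and the window are for the sponsor to settle.
- **In Section 8.5**, name the pre-coil measurement that serves as baseline for crossover subjects. Report 12- and 36-month FEV1 change separately for randomized Treatment and crossover subjects, and flag crossover subjects without a new pre-coil PFT.

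The cost is amendment wording, a small additional descriptive analysis, and site burden for tests in up to 40 Controls that Section 4.3 already presupposes. For Controls already implanted, only the separate reporting and the flag can still be applied.

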4.4 Subject Withdrawal

Subjects are free to withdraw from the study at any time and will be withdrawn if they inform their PI that they no longer wish to participate or if they become lost to follow-up. The investigator may withdraw a subject at any time for safety or non-compliance with the protocol. Subject's Withdrawal will be recorded in the EDC system along with the relevant reason(s) for study exit (lost to follow-up, withdrawn by investigator, or withdrawn by subject). Data collected prior to the subject's withdrawal will remain part of the study record, unless country specific data protection regulations prohibit it.

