6.4.4 Patient completion or early withdrawal

Subjects who receive the Treatment procedure complete the study 36 months after the initial implant procedure or when they choose to withdraw from the study, if earlier than 36 months post-procedure. In the event of a continuing SAE related to the Coil system, the subject will be asked to return for follow-up until the SAE has resolved or is deemed to be continuing indefinitely. Control subjects who do not crossover to treatment will exit the study immediately.

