7.2 Recording Adverse Events (AE)

Subjects will be required to report AEs of interest. At each study visit, site staff will ask general, open-ended, non-directed questions to obtain information about AEs. If the subject is unable to attend a trial visit, AEs can be collected by telephone contact. At any time during the study, the Subject may volunteer information that meets the definition of an AE.

The investigator should record all SAEs and specific Respiratory AEs of interest in the eCRFs. Below is a list of specific Respiratory AEs of interest that should be recorded:

- COPD Exacerbation
- Hemoptysis
- Pneumothorax
- Lower Respiratory Tract Infection/Pneumonia
- Tissue Reaction, Localized (a.k.a. Coil Associated Inflammatory response syndrome (CAIRs), also called Coil Associated Opacity (CAO) in the IFU)

Investigators will obtain all the information required to complete the AE form. Where possible, a diagnosis, rather than a list of signs or symptoms, should be recorded. Any medical management of an event and the resolution of an event must be recorded in source documentation and on the appropriate eCRF using medical terminology according to sponsor instructions.

For each SAE and specific respiratory AEs of interest, the following information will be recorded at a minimum:

- AE term
- Serious/non-serious
- Severity
- Action taken
- Relationship to Coil System
- Expected/Unexpected
- Date and time of onset
- Date and time of resolution

Was the subject withdrawn from the study due to the AE

Any SAE experienced by a subject will be followed until the SAE has resolved to the PI's or sub-investigator's satisfaction or is considered stable. If a problem still exists, then the PI or sub-investigator at his/her discretion will ask the subject to come back to the clinic for further evaluation. SAEs should be managed as discussed in Section 7.5.

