8.6 Safety Analyses

Safety analyses will be conducted on the safety population defined as those Subjects who enter the bronchoscopy suite for the initial Coil procedure. AE and SAEs will be summarized by treatment group based on MedDRA codes. Incidence rates through 6 months will be summarized for treatment and control groups. For coil treated subjects, events will also be summarized by relevant, discrete time periods including the Treatment recovery period (30 days from either treatment), as well as through the 12- and 36-month follow-up periods.

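### Investigator withdrawal after implant counts as study exit with no later collection of new events or deaths, so 12- and 36-month harm is liable to be understated

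*Combined protocol and SAP*

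**What the plan says.** Protocol 4.4 provides that "The investigator may withdraw a subject at any time for safety or non-compliance with the protocol". The rule does not distinguish before from after implant. The reason is entered in the EDC as one for "study exit (lost to follow-up, withdrawn by investigator, or withdrawn by subject"), so an investigator's withdrawal has the same status as a subject's own. On data, 4.4 says only this: "Data collected prior to the subject's withdrawal will remain part of the study record", subject to national data-protection law.

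Other sections bear on what happens next:

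- **5.1.2** lets the investigator restrict treatment to one lung when the second side is contraindicated. It does not call this study exit.
- **6.4.4** has treated subjects finish at 36 months or when they themselves choose to leave. It does not mention withdrawal by the investigator. For a continuing Coil-related SAE, "the subject will be asked to return for follow-up until the SAE has resolved or is deemed to be continuing indefinitely".
- **7.2** has any SAE followed until it resolves or is stable, with no limit to related events. It allows AEs to be collected by telephone when a visit cannot be attended. The AE form asks "Was the subject withdrawn from the study due to the AE".
- **6.5.12** permits coil removal only for a medical reason. Study exit does not trigger it.
- **8.3 and 8.6** run the safety analyses on all randomized subjects who enter the bronchoscopy suite, with events in coil-treated subjects summarised by discrete periods "as well as through the 12- and 36-month follow-up periods".

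**The concern.** After the last procedure, leaving the study does not change exposure: the coils stay in. It changes only what is observed. The second procedure falls about 2 months after the first, and the only visits after it are at 12 and 36 months. A subject withdrawn soon after the second procedure can therefore lose up to about 36 − 2 = 34 months of planned observation.

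The loss is unlikely to be random. Withdrawal for safety selects on harm by its nature. Withdrawal for non-compliance may do so too. The 12- and 36-month visits have a ±4-week window but are meant to fall after 30 stable days, and subjects with frequent exacerbations will find that hardest to meet.

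The primary objective includes confirming the safety profile. Controls either cross over or leave, so there is no concurrent arm at 12 or 36 months. The absolute incidence in coil-treated subjects is then the long-term safety evidence, and nothing offsets events missed after an investigator-imposed exit.

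**Working it through.** **Step 1. What is collected after an investigator withdrawal, read across sections.**

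| Item | Provided for after exit? | Where |
|---|---|---|
| Event that prompted withdrawal | Yes, if an SAE or a respiratory AE of interest | 7.2 |
| Continuing SAE, Coil-related | Yes | 6.4.4, 7.2 |
| Continuing SAE, judged unrelated | Yes under 7.2; not covered by 6.4.4 | 7.2 |
| New SAE or new respiratory event of interest | No provision found | – |
| Later death not arising from a followed SAE | No provision found | – |
| 12- and 36-month PFT and HRCT | No provision found | – |

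The sections also disagree. 6.4.4 and 7.2 differ on which SAEs are followed, 6.4.4 omits investigator withdrawal, and the synopsis stops AE follow-up at study completion or termination.

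**Step 2. Direction and possible size.** The plan gives no figure to reproduce here: no withdrawal rate, event rate, censoring rule or person-time method. The 120 randomized split 80 and 40 as 2:1 requires, but the number who will be coil-treated is not known, because controls may not cross over (4.3). Every input below is an assumption.

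- w: share of implanted subjects withdrawn at month 6 (5–20%)
- p: 36-month incidence in retained subjects (20% or 40%)
- k: hazard ratio after exit in withdrawn subjects (0.5–4)
- constant hazards, equal in both groups up to month 6; no first event after exit is collected

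Formulas:

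- incidence in withdrawn subjects before exit: o = 1 − (1−p)^(6/36)
- their incidence by month 36: q = 1 − (1−p)^((6+30k)/36)
- true incidence = (1−w)p + wq
- (a) crude, full safety population = (1−w)p + wo, so the shortfall is w(q−o)
- (b) Kaplan-Meier, censored at exit = p
- (c) evaluable subjects only = [(1−w)p + wo] / [1 − w(1−o)]

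Example with p = 20%, w = 10%, k = 2:

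- o = 1 − 0.8^(6/36) = 0.0365 and q = 1 − 0.8^(66/36) = 0.336
- true = 0.180 + 0.0336 = 21.4%
- (a) 0.180 + 0.0037 = 18.4%, short by 0.10 × (0.336 − 0.0365) = 3.0 points
- (b) 20.0%, short by 1.4 points
- (c) 0.1837 / 0.9037 = 20.3%, short by about 1 point

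Varying only k (p = 20%, w = 10%, 36 months):

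| k | True | (a) Crude | (b) Kaplan-Meier | (c) Evaluable |
|---|---|---|---|---|
| 0.5 | 19.2% | 18.4% | 20.0% | 20.3% |
| 1 | 20.0% | 18.4% | 20.0% | 20.3% |
| 2 | 21.4% | 18.4% | 20.0% | 20.3% |
| 4 | 23.4% | 18.4% | 20.0% | 20.3% |

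Error at 36 months over the whole assumed range:

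| Method | p = 20% | p = 40% |
|---|---|---|
| (a) | 0.4 to 10.1 points too low | 0.9 to 15.0 points too low |
| (b) | 1.6 too high to 6.8 too low | 2.8 too high to 8.7 too low |
| (c) | 2.3 too high to 6.1 too low | 4.0 too high to 7.5 too low |

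The largest figure under (a) is 0.20 × (0.833 − 0.082) = 0.150. At 12 months, method (a) is too low by about 0.1 to 5.3 points.

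**The case against.** The plan has more safeguards than 4.4 alone suggests. A reader might infer that withdrawal ends all data collection. The documents do not support that. The 4.4 sentence on earlier data is a retention clause and does not refuse later data. 7.2 follows any SAE already experienced, related or not, so a death arising from it should be captured. A reader might also take the AE-form question as a sign that safety withdrawals are expected. It is only a data item, and it makes such withdrawals visible. Nor is a subject too ill to attend lost for that reason alone, since 7.2 allows telephone collection. And 5.1.2 already lets treatment stop after one side without study exit. All of this stands, and it narrows the gap to new events, later deaths and the late assessments.

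On bias, understatement is certain only for a crude proportion over the full safety population, and only if events occur after exit. Under (b) and (c) it needs withdrawn subjects to be at higher later risk, which is plausible but not shown. Section 8.2 refers to a separate SAP whose text was not available for this check, so a denominator or censoring rule may exist there. Such a rule would settle the direction but would not recover events that were never collected.

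Finally, holding subjects withdrawn for safety to the full 12- and 36-month schedule, with PFT and HRCT, would override the investigator's judgement about study tests. That objection also stands and limits the remedy.

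**Conclusion.** The point holds in this form. Investigator withdrawal is study exit even after implant, and nothing provides for new safety events or vital status afterwards. The only denominator the available text states for the safety analyses is the full safety population, with no censoring rule. On that reading, each uncollected first event after exit lowers the reported 12- or 36-month incidence.

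The stronger statement, that long-term harm is understated by a known amount, is not supported. The documents give neither the number withdrawn nor their later risk, and the percentages above only show how the result behaves under assumed inputs. They are an upper reading for deaths, because some deaths would be caught through follow-up of SAEs already present. The weakness should be corrected because the remedy is cheap and the 12- and 36-month figures have no control arm. It does not invalidate the trial.

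**What to change.** Reconcile 4.4, 6.4.4, 7.2 and the synopsis text on AE follow-up so that they say the same thing:

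1. Separate an investigator's decision to stop further Coil procedures or study tests from the end of follow-up. The decision itself stays with the investigator, as now.
2. After any implant, let only withdrawal of consent or loss to follow-up end data collection.
3. Keep subjects withdrawn by the investigator under collection of SAEs, respiratory AEs of interest and vital status to 36 months, using the telephone contact 7.2 already allows. PFT and HRCT are done only if the investigator considers them appropriate.
4. Split the AE-form question into two: no further Coil procedure because of the AE, and left the study.
5. State the denominator and censoring rule for the 12- and 36-month summaries, and report the number withdrawn by the investigator beside them.

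The cost is a protocol amendment needing sponsor, investigator and ethics committee approval (10.7) at up to 30 sites, one eCRF change and a few telephone calls. Randomization is described as complete, so the change helps only subjects still in follow-up, or those already withdrawn who agree to contact. Some will decline.
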